3.4 Risk Reduction Metrics

- Absolute Risk Reduction (ARR) and Number Needed to Treat (NNT):
 - ARR will be calculated from survival curves to quantify the benefit of Cerebrolysin in reducing HT risk.
 - NNT will be derived from ARR to estimate the number of patients needing treatment to prevent one HT event.
- Restricted Mean Survival Time (RMST):
 - RMST differences between treatment groups will be calculated, providing an alternative to HRs for assessing survival benefit.

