This analysis aims to evaluate the timing of anticoagulation resumption in MCA stroke patients treated with Cerebrolysin, stratified by hemorrhagic transformation (HT) risk. The primary focus is on determining Cerebrolysin's effect on the incidence and hazard of HT over time and establishing the optimal timing for anticoagulation resumption using advanced survival and hazard-based methods. Patients will be categorized into low-risk (HTI = 0) and high-risk (HTI > 0) groups based on the Hemorrhagic Transformation Index (HTI) scores, and outcomes will be analyzed for both symptomatic and any HT within 14 days.

2. Objectives and Endpoints

- **Primary Objective**: To evaluate the effect of Cerebrolysin on the timing of safe anticoagulation resumption in stroke patients with varying HT risk levels.
- Primary Endpoints:
 - Incidence of **any HT** and **symptomatic HT** over 14 days.
 - **Timing of Anticoagulation Resumption**: Defined by inception points based on hazard deceleration (HD) curves.

• Secondary Endpoints:

- \circ Survival probabilities for HT stratified by HT risk groups (HTI = 0 vs. HTI > 0).
- Hazard and risk reduction metrics, including hazard ratios (HR), absolute risk reduction (ARR), number needed to treat (NNT), and restricted mean survival time (RMST) differences for symptomatic and any HT.

3. Statistical Analysis

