3.2 Survival Analysis

• Nonparametric Analysis:

- Kaplan–Meier survival curves will be generated for symptomatic and any HT, stratified by HT risk group and treatment arm. Log-rank tests will compare survival distributions.
- The proportional hazard (PH) assumption will be tested using graphical diagnostics and statistical methods, with alternative combined permutation tests if the assumption is violated.

• Semiparametric Analysis:

- Cox proportional hazards models will estimate hazard ratios (HRs) for symptomatic and any HT, adjusting for HTI category and treatment group.
- If the PH assumption is violated, time-dependent Cox models with time-varying covariates will be employed.

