3.3 Parametric Analysis and Model Selection

• Parametric Survival Models:

- Candidate models include Gompertz, Weibull, exponential, log-logistic, lognormal, and Royston–Parmar flexible parametric models. Model fit will be assessed using the Akaike Information Criterion (AIC), Bayesian Information Criterion (BIC), and Cox–Snell residual plots.
- The model providing the best fit will be used to estimate hazard rates, survival probabilities, and restricted mean survival times.

• Hazard Deceleration (HD) Analysis:

- HD curves will be derived from the parametric hazard function, capturing changes in hazard rates over time.
- Inception points for anticoagulation resumption will be identified based on HD values falling below 5% of the initial hazard peak, indicating stabilization of HT risk.

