3.5 Subgroup and Sensitivity Analyses

- Subgroup Analysis:
 - Separate analyses for low-risk (HTI = 0) and high-risk (HTI > 0) groups will examine Cerebrolysin's effects across HT risk strata.
- Sensitivity Analysis:
 - Parametric and semiparametric models will be compared using the Hausman specification test to ensure model consistency and robustness.

4. Software and Statistical Significance

- **Software**: Stata/SE v.17.0.
- **Significance Level**: α = 0.05 for primary and secondary analyses, with multiple hypothesis correction using the Romano-Wolf adjustment.

5. Interpretation and Reporting

- Clinical Implications:
 - Findings will inform optimal anticoagulation timing in stroke patients treated with Cerebrolysin, stratified by HT risk.
- Reporting:
 - Results will be reported with corresponding HRs, ARR, NNT, and RMST differences, stratified by HTI categories. Visualizations will include Kaplan–Meier curves, hazard plots, and survival curves for clarity.

6. Limitations

• This analysis relies on post hoc stratification, which may introduce selection bias. Results should be interpreted cautiously and validated in prospective studies.

This SAP outlines a robust framework for analyzing the impact of Cerebrolysin on HT incidence and anticoagulation timing in ischemic stroke patients, ensuring methodological rigor and clinical relevance.

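### Part III takes ARR and NNT for HT from survival curves without saying how death before HT is handled or which curve is used; day-14 cumulative incidence is the suitable basis.

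*SAP*

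**What the plan says.** Part III is the survival analysis added to the SAP on 25 April 2024. Its introduction sets the horizon: "outcomes will be analyzed for both symptomatic and any HT within 14 days".

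Two kinds of survival curve are planned.
- Section 3.2 (Survival Analysis): "Kaplan–Meier survival curves will be generated for symptomatic and any HT, stratified by HT risk group and treatment arm". It adds that "Log-rank tests will compare survival distributions" and plans Cox models for both HT outcomes.
- Section 3.3 (Parametric Analysis and Model Selection): "The model providing the best fit will be used to estimate hazard rates, survival probabilities, and restricted mean survival times".

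Section 3.4 (Risk Reduction Metrics) then says "ARR will be calculated from survival curves to quantify the benefit of Cerebrolysin in reducing HT risk" and "NNT will be derived from ARR to estimate the number of patients needing treatment to prevent one HT event". It also plans RMST differences between arms. Section 3.5 repeats the analysis by risk group: "Separate analyses for low-risk (HTI = 0) and high-risk (HTI > 0) groups will examine Cerebrolysin's effects across HT risk strata".

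Part III contains no censoring rule, no rule for death before HT, no cumulative incidence function and no competing-risk model. Section 3.4 does not say which of the two curves supplies the ARR.

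**The concern.** HT is a non-fatal event, observed here over the 14 days after an acute stroke. A patient who dies without HT can no longer have it. If that death is censored, as standard software does unless told otherwise, the patient is treated as still able to develop HT later. One minus the survival curve is then at or above the proportion of patients who actually have HT by day 14. This applies to Kaplan–Meier and to the listed parametric models alike, so choosing between them does not remove the problem.

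For hazard ratios this is a matter of labelling, because a Cox model with deaths censored estimates the cause-specific hazard ratio. ARR and NNT are absolute quantities. The number of patients to treat to prevent one HT must come from the incidence in patients who can die. Section 5 of Part III lists ARR, NNT and RMST among the results to be reported by HTI category. The plan's own check, a Hausman comparison of parametric and semiparametric models, cannot detect the problem because both models would share the same censoring.

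**Working it through.** The SAP states no ARR, NNT, event count or mortality, so there is no figure of its own to reproduce. The check asks how far one minus the survival curve moves from the true incidence.

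**Inputs from the SAP (Part I, section 4; Part III, section 1).** Control HT 20%, target OR 0.5, horizon 14 days.

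**True values implied.** Control odds 0.20/0.80 = 0.25. Cerebrolysin odds 0.5 × 0.25 = 0.125, so risk 0.125/1.125 = 11.1%. ARR = 20.0 − 11.11 = 8.89 points; NNT = 1/0.0889 = 11.25.

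**Assumed input.** D, the proportion dying without HT by day 14, is varied because the SAP gives no value. F is the true proportion with HT by day 14.

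**Model A, HT and death hazards constant over 14 days.** With deaths censored, the curve estimates 1 − (1 − F − D)^(F/(F + D)).
- D = 5%, control: 1 − 0.75^(0.20/0.25) = 20.56%. Cerebrolysin: 1 − 0.8389^(0.1111/0.1611) = 11.41%. ARR 9.15 points.
- D = 10%, control: 1 − 0.70^(0.20/0.30) = 21.16%. Cerebrolysin: 1 − 0.7889^(0.1111/0.2111) = 11.73%. ARR 9.43 points.

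**Model B, all HT in days 0–3, constant death hazard to day 14.** With HT hazard λ, death hazard μ and a = λ + μ, solve numerically:
- F = (λ/a)(1 − e^(−3a))
- D = (μ/a)(1 − e^(−3a)) + e^(−3a)(1 − e^(−11μ))

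The curve then estimates 1 − e^(−3λ). For D = 10% this gives 20.27% and 11.25%, ARR 9.02 points.

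| Death without HT (control / Cerebrolysin) | ARR, points (B to A) | NNT (B to A) | Relative change in ARR |
|---|---|---|---|
| none | 8.89 | 11.25 | 0 |
| 5% / 5% | 8.95 to 9.15 | 11.2 to 10.9 | +0.7% to +2.9% |
| 10% / 10% | 9.02 to 9.43 | 11.1 to 10.6 | +1.5% to +6.1% |
| 15% / 15% | 9.09 to 9.74 | 11.0 to 10.3 | +2.3% to +9.6% |
| 10% / 5% | 9.09 to 9.75 | 11.0 to 10.25 | +2.3% to +9.7% |
| 5% / 10% | 8.88 to 8.83 | 11.26 to 11.33 | −0.1% to −0.7% |

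**Risk strata.** The SAP gives no HT rates by HTI group. Assume 8% versus 4.2% in the low-risk group and 35% versus 21.2% in the high-risk group (OR 0.5 in each), with 10% death without HT everywhere.
- Low risk: true ARR 3.83 points, curve 3.88 to 4.05; excess 0.05 to 0.22 points, or 1.3–5.6% relative.
- High risk: true ARR 13.79 points, curve 14.05 to 14.73; excess 0.26 to 0.94 points, or 1.9–6.9% relative.

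The absolute excess is larger in the high-risk group, but the relative excess is similar. A clear relative difference needs higher mortality in that group: with 2% death in the low-risk group it becomes 0.2–1.1% against 1.9–6.9%.

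**The case against.** The strongest defence has four parts.

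*The SAP never says that deaths are censored.* This is correct. A reader may infer such a rule, but it comes from silence and from software defaults. Keeping patients who die without HT as event-free to day 14 would make one minus Kaplan–Meier equal the cumulative incidence. That is itself a competing-risk convention, though, and the SAP would have to state it. It would also make RMST count days after death as HT-free, which sits badly with section 3.4 presenting RMST as a measure of survival benefit.

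*The effect is small.* This also stands. At equal death of up to 15% the NNT falls by less than one patient. Section 3.3 of Part III expects an initial hazard peak, which points towards early HT and so towards the lower end of each range if deaths are more evenly spread.

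*The stronger claims are not shown.* A reader might infer that bias is worst in the HTI > 0 group because early deaths concentrate there, or that the ARR must be overstated. The SAP gives no mortality by stratum or arm. The first is plausible in absolute points only under assumed rates, and the second fails when deaths are more frequent on Cerebrolysin.

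*The tests are sound, and the metrics are secondary.* A log-rank test with deaths censored validly compares cause-specific hazards, so replacing it with Gray's test would be a preference. ARR, NNT and RMST are secondary endpoints of an added analysis. The main HT comparison in Part I is logistic regression on HT within 14 days, which does not use these curves.

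What remains is the estimator. Choosing the basis of the ARR is the SAP's task, and Part III leaves it open between two curves that share the same weakness under default censoring.

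**Conclusion.** The point holds as a modest one about the basis of ARR and NNT. The plan takes both from survival curves for a non-fatal event, without a rule for death before HT and without naming the curve. If deaths are censored, the planning-rate ARR of 8.89 points would be read as about 8.95–9.43 and the NNT of 11.25 as about 11.2–10.6, for 5–10% death without HT in both arms. These sizes rest on assumed mortality and on the two hazard patterns shown. With few deaths the effect is negligible; with unequal deaths it can go either way. The documents do not establish that deaths are censored, that the HTI > 0 group is affected most, or that the log-rank and Cox analyses are wrong.

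**What to change.** In Part III, section 3.4, compute ARR and NNT from the Aalen–Johansen cumulative incidence of HT at day 14, by arm and HTI group, with death before HT as a competing event. Plot HT risk from the same estimate. State explicitly how deaths without HT enter each analysis.

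In section 3.2, keep the log-rank test and Cox models and label their results as cause-specific.

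State whether RMST refers to HT-free survival, with HT or death as the event, or to time lost to HT from the cumulative incidence. These answer different questions, so this is a choice of estimand that the SAP should record.

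The cost is a few sentences, standard software commands and the dates of death within 14 days. The stated ARR will usually be slightly smaller.

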3.5 Subgroup and Sensitivity Analyses

- Subgroup Analysis:
 - Separate analyses for low-risk (HTI = 0) and high-risk (HTI > 0) groups will examine Cerebrolysin's effects across HT risk strata.
- Sensitivity Analysis:
 - Parametric and semiparametric models will be compared using the Hausman specification test to ensure model consistency and robustness.

4. Software and Statistical Significance

- **Software**: Stata/SE v.17.0.
- **Significance Level**: α = 0.05 for primary and secondary analyses, with multiple hypothesis correction using the Romano-Wolf adjustment.

5. Interpretation and Reporting

- Clinical Implications:
 - Findings will inform optimal anticoagulation timing in stroke patients treated with Cerebrolysin, stratified by HT risk.
- Reporting:
 - Results will be reported with corresponding HRs, ARR, NNT, and RMST differences, stratified by HTI categories. Visualizations will include Kaplan–Meier curves, hazard plots, and survival curves for clarity.

6. Limitations

• This analysis relies on post hoc stratification, which may introduce selection bias. Results should be interpreted cautiously and validated in prospective studies.

This SAP outlines a robust framework for analyzing the impact of Cerebrolysin on HT incidence and anticoagulation timing in ischemic stroke patients, ensuring methodological rigor and clinical relevance.

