The CEREHETIS trial is a prospective, randomized, open-label, multicenter, parallel-group, phase IIIb pilot study with an active control. Patients are randomized in a 1:2 ratio to receive either IVT alone or IVT with Cerebrolysin.

4. Sample Size Calculation

- **Primary Endpoint (HT Rate)**: Based on the assumption that 20% of control group patients will experience HT, with a target odds ratio (OR) of 0.5 in the Cerebrolysin group.
- Significance Level: 0.05
- **Power**: 80%
- Dropout Rate: 10%
- **Design:** 1:2 allocation ratio between the intervention and control groups to optimize power efficiency and minimize required sample size for this pilot study.

5. Randomization and Blinding

- **Randomization**: Simple randomization across centers using Bernoulli variates (probability parameter of 0.333), with sealed opaque envelopes for treatment allocation.
- **Blinding**: Due to the distinct yellow color of Cerebrolysin, treatment blinding was not feasible; however, imaging analyses are blinded.

6. Data Collection and Time Points

Data collection occurs at the following time points:

- Baseline (Day 0): Demographic data, NIHSS, CT, DTI baseline imaging
- Day 1: Follow-up imaging and NIHSS assessment
- Day 7 and Day 14: NIHSS score, follow-up CT, and DTI imaging on day 14
- Day 90: Modified Rankin Scale (mRS) assessment for functional outcome

7. Statistical Analysis

a. Descriptive Statistics

- **Continuous Variables**: Presented as median (M) and interquartile range (IQR) due to non-normal distributions.
- **Categorical Variables**: Presented as percentages and analyzed with χ^2 -tests.

b. Comparative Analysis

- Primary Analysis (HT Rates):
 - Comparison of HT Rates: Logistic regression will compare the rates of any and symptomatic HT between the Cerebrolysin and control groups. Odds ratios (OR) with 95% confidence intervals (CI) will be reported.
 - Adjustment for Confounders: Age, NIHSS, ASPECTS score, and baseline variables such as history of hypertension and previous stroke will be included in multivariate models to control for potential confounding.
- Secondary Analysis:
 - **Neurological Recovery (NIHSS)**: The Mann–Whitney U test will compare NIHSS scores between groups at day 1 and day 14.
 - **Functional Outcome (mRS)**: The mRS scores on day 90 will be assessed using a χ^2 -test for favorable outcomes (mRS ≤ 2). Additionally, a shift analysis will be conducted to evaluate distributional differences in mRS scores between groups.

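### Part III examines treatment effects by HTI group only through separate analyses, with no treatment-by-HTI interaction, so a result in one stratum says little about a true difference

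*SAP*

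**What the plan says.** Part III, section 3.5 (Subgroup and Sensitivity Analyses) relies on "Separate analyses for low-risk (HTI = 0) and high-risk (HTI > 0) groups" to show how the effect of Cerebrolysin varies with HT risk. The Cox model in section 3.2 is described as "adjusting for HTI category and treatment group", which names two main effects and no product term. Section 3.2 also splits the Kaplan–Meier curves by risk group and arm. Under section 5 (Interpretation and Reporting), "Results will be reported with corresponding HRs, ARR, NNT, and RMST differences, stratified by HTI categories".

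The HT endpoint in section 2 is "Incidence of any HT and symptomatic HT over 14 days", so there are two event types and two strata. Section 4 sets alpha at 0.05 "with multiple hypothesis correction using the Romano-Wolf adjustment", without defining the family of hypotheses. Section 6 adds a general caution about post hoc stratification.

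Part II, section 3.6, does assess heterogeneity across HTI subgroups with I² and H², but in a separate subgroup meta-analysis built on binary outcomes. Part III does not refer to it.

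**The concern.** Section 3.5 has a comparative aim: how the effect varies with HT risk. Two unconnected fits do not address it, and a main-effects Cox model assumes one HR for both groups. Without a planned contrast, a reader is left to set one stratum's significance against the other's non-significance. That pattern can arise from chance and unequal event numbers when the true HRs are equal. Part III intends its findings to inform anticoagulation timing separately by HT risk, so a spurious contrast between strata would carry weight.

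**Working it through.** The SAP states no sample size, event count or stratum power, so there is no figure of its own to reproduce.

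**Inputs.** The sample size in Part I, section 4, rests on an "assumption that 20% of control group patients will experience HT, with a target odds ratio (OR) of 0.5 in the Cerebrolysin group". Alpha in that section is 0.05 (two-sided assumed) and power is 80%. Section 3 of Part I sets control to Cerebrolysin at 1:2, while section 4 words the ratio the other way round. Both directions are computed.

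**Design effect.** Control odds are 0.2/0.8 = 0.25. Halved, they are 0.125, a rate of 0.125/1.125 = 11.1%. Under proportional hazards HR = ln(1 − 0.111)/ln(1 − 0.2) = 0.528, so |ln HR| = 0.639.

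**Events.** The pooled two-proportion formula gives the evaluable numbers:
- Control to Cerebrolysin 1:2: 189 + 378 = 567 patients; events 189 × 0.2 + 378 × 0.111 = 79.8, about 80.
- Reverse ratio: 401 + 201 = 602 patients; events 401 × 0.2 + 201 × 0.111 = 102.5, about 102.

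**Power per stratum.** By Schoenfeld's formula, power = Φ(√(d × 1/3 × 2/3) × |ln HR| − 1.96) for d events. Take 80 events split 80/20. In HTI > 0, d = 64: √(64 × 2/9) × 0.639 − 1.96 = 0.45, power 0.673. In HTI = 0, d = 16: 1.886 × 0.639 − 1.96 = −0.76, power 0.225. Then P(exactly one significant) = 0.673 × 0.775 + 0.225 × 0.327 = 0.595.

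Any HT, HR 0.528 in both strata, unadjusted alpha 0.05 (event split assumed):

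| Share of events in HTI > 0 | 80 events: exactly one / both / neither | 102 events: exactly one / both / neither |
|---|---|---|
| 50% | 50 / 23 / 27% | 49 / 33 / 18% |
| 70% | 54 / 19 / 26% | 55 / 28 / 17% |
| 80% | 60 / 15 / 25% | 63 / 21 / 16% |
| 90% | 66 / 10 / 24% | 72 / 13 / 15% |
| 95% | 70 / 7 / 23% | 77 / 8 / 14% |

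**Sensitivity.** Range for exactly one stratum significant, over the same splits:
- Alpha 0.05/4 = 0.0125, the Bonferroni bound for two endpoints in two strata: 40-55% (80 events), 46-67% (102 events).
- HR 0.6, alpha 0.05: 44-55% and 48-64%.
- HR 0.7, alpha 0.05: 30-33% and 35-40%.

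**Symptomatic HT.** If it is 20-50% of 80 any-HT events (16 to 40 events, assumed) and HR is 0.53, exactly one stratum is significant in 23-45% of trials and neither in 51-75%. The ordering weakens with more events. At 51 events (half of 102), split evenly, power is Φ(√(25.5 × 2/9) × 0.639 − 1.96) = 0.33 per stratum, so neither (0.67² = 45%) and exactly one (2 × 0.33 × 0.67 = 44%) are about level.

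**Simulation check.** Log-rank simulation with 567 patients, 1:2 allocation, identical HRs, 4,000 runs per scenario and 50-90% of events in HTI > 0 found exactly one stratum significant in 50-71% of trials. An interaction test declared a difference in about 6-7% of the same trials.

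**Power of the interaction test.** SE(ln ratio of HRs) = √(1/(2d₁/9) + 1/(2d₂/9)). With 80 events split 40/40, SE = 0.474, and 80% power needs a ratio of exp(−2.80 × 0.474), about 0.27. Split 64/16, SE = 0.593 and the ratio is about 0.19.

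**The case against.** A reader might infer that Part III will usually report an effect in one stratum only. The document does not support that as a general statement. It needs the full design effect, any HT rather than symptomatic HT, and no multiplicity correction. With a common HR of 0.7 the likeliest result is significance in neither stratum. Section 4 does plan Romano-Wolf, which lowers the frequency. It does not, however, turn a contrast between significant and non-significant into a test of difference.

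Nor does the SAP bound the events in each stratum. The totals are back-calculated from Part I, whose objective concerns ischemic stroke patients given thrombolysis, while Part III speaks of MCA stroke; whether these are the same patients is unclear. Few events in HTI = 0 is an inference from the low-risk label, since a large low-risk group could still contribute many. It is also tempting to say that symptomatic HT makes the problem worse. Power is worse, but one-stratum results become less frequent.

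The SAP has no rule that declares a differing effect from stratum p-values. It promises effect estimates by HTI category and urges caution. Part II is devoted to effect heterogeneity by HT risk. These points stand, but none gives Part III a between-stratum comparison. Part II's heterogeneity statistics do not cover Part III's HRs, and section 6 warns of selection bias, which is a different problem.

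**Conclusion.** The point holds in this form: Part III plans no valid comparison of the treatment effect between HTI = 0 and HTI > 0 for its time-to-event outcomes. At the design effect, equal HRs would still leave any HT significant in exactly one stratum about as often as not, or more often, and both strata would be significant together in at most about a third of trials. The figures assume that Part I's rates carry over to Part III, that tests are two-sided, and that the event split lies between 50/50 and 95/5. The contradictory allocation direction moves the numbers but not the conclusion. The flaw affects how the stratum results can be read, not the trial's primary result, and should be corrected.

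**What to change.** In Part III, sections 3.2 and 3.5, fit one Cox model, and one model of the selected parametric form, to all patients with treatment, HTI group and their interaction. Take the stratum HRs with 95% CIs from that model. Report the interaction as a ratio of HRs with its 95% CI, and state that any claim of an effect differing by HTI rests on that estimate, not on the stratum p-values.

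The cost is a few sentences of SAP text; the data and software are unchanged. The downside is the low power shown above. The CI for the ratio will be wide, and the SAP should say that a non-significant interaction is not evidence of equal effects.

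### Part III's Hausman check contrasts different parameters if a log-logistic or lognormal model is selected, and even for a PH-metric model it cannot establish robustness.

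*SAP*

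**What the plan says.** Part III, 3.2 makes the semiparametric model a Cox model: "Cox proportional hazards models will estimate hazard ratios (HRs) for symptomatic and any HT, adjusting for HTI category and treatment group". If proportional hazards (PH) fail, it changes model: "If the PH assumption is violated, time-dependent Cox models with time-varying covariates will be employed".

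Part III, 3.3 lists six parametric families: "Candidate models include Gompertz, Weibull, exponential, log-logistic, lognormal, and Royston–Parmar flexible parametric models". Selection is by AIC, BIC and Cox-Snell plots, after which "The model providing the best fit will be used to estimate hazard rates, survival probabilities, and restricted mean survival times". The hazard deceleration curves and the inception points also come from the parametric hazard.

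Part III, 3.5 then gives the single item labelled as a sensitivity analysis: "Parametric and semiparametric models will be compared using the Hausman specification test to ensure model consistency and robustness".

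The plan does not name the coefficient to be compared, the metric of the parametric model, the scale of the Royston-Parmar model, or the action if the test rejects. It does not say whether only the selected model enters the test. Nothing excludes log-logistic or lognormal models from it.

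**The concern.** A Hausman test needs two estimators of the same parameter, one of them efficient under the null hypothesis. Its statistic is the squared difference of the estimates divided by the difference of their variances. Two of the six candidates, log-logistic and lognormal, are accelerated failure time (AFT) models and not PH models. Their treatment coefficient is a log time ratio, positive when treatment delays HT. The Cox coefficient is a log hazard ratio, negative in the same situation. Setting one against the other does not test specification.

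For a PH-metric model the two coefficients do match. The question then is whether a contrast of treatment coefficients can support what Part III most needs from the parametric model, which is the shape of the hazard over 14 days.

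At stake is a check that may fail to compute, reject on trivial differences, or pass without having examined the hazard curve behind the inception points.

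**Working it through.** **Inputs from the SAP.** Part I, section 4: "Based on the assumption that 20% of control group patients will experience HT, with a target odds ratio (OR) of 0.5 in the Cerebrolysin group". This gives odds of 0.5 x 0.20/0.80 = 0.125, so a Cerebrolysin risk of 0.125/1.125 = 11.1%. Under PH the hazard ratio is ln(1 - 0.111)/ln(1 - 0.20) = 0.1178/0.2231 = 0.53. HT is followed for 14 days.

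**Assumptions, not in the SAP.** Weibull shape 0.5, log-logistic scale 2, lognormal scale 3, two thirds on Cerebrolysin. N = 40,000 for limiting values, and 400 replicates of N = 400 for the test. The SAP states no sample size or Hausman result, so there is no plan figure to reproduce.

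**Statistic.** H = (b_Cox - b_par)^2 / (V_Cox - V_par), treatment coefficient only, referred to chi-squared with 1 df (critical value 3.841).

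**Step 1: do the coefficients match?** Limiting values at N = 40,000:

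| True distribution | Cox log HR | Weibull PH log HR | Log-logistic log time ratio | Lognormal log time ratio |
|---|---|---|---|---|
| Weibull | -0.654 | -0.654 | +1.359 | +1.530 |
| Log-logistic | -0.617 | -0.618 | +1.309 | +1.487 |
| Lognormal | -0.655 | -0.657 | +1.018 | +1.142 |

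Cox and Weibull PH agree. The AFT coefficients have the opposite sign and another scale. The metric matters even within one family: a Weibull model written in AFT form has log time ratio -ln(HR)/shape. With the simulated HR of 0.529 this is 0.637/0.5 = +1.27.

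**Step 2: is the AFT statistic defined?** In the Weibull run the HT rates were 20.5% and 11.3%. That is about 40,000 x 1/3 x 0.2054 = 2,739 and 40,000 x 2/3 x 0.1127 = 3,005 events. The Cox variance is roughly 1/2,739 + 1/3,005 = 0.0007. The AFT variances were 0.0033 (log-logistic) and 0.0044 (lognormal). The differences are 0.0007 - 0.0033 = -0.0026 and 0.0007 - 0.0044 = -0.0037, so H is undefined. At N = 400 the difference was negative in 400/400 replicates for both AFT models under all three truths.

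A run with 540 patients, shape 0.4 and one third treated also gave a negative difference in 100% of replicates (mean Cox -0.65, mean lognormal +1.82). The sign is not universal. With a lognormal-shaped baseline and truly proportional hazards, the difference was almost always positive and the test rejected in 93 to 95% of runs. Either way the result says nothing about robustness.

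**Step 3: could an AFT model be selected?** Among Weibull PH, log-logistic and lognormal only, AIC chose an AFT model in:
- 222/400 replicates (56%) under Weibull truth;
- 260/400 (65%) under log-logistic truth;
- 355/400 (89%) under lognormal truth.

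These frequencies depend on the assumed settings and on comparing three families, not six.

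**Step 4: how does the test behave for PH-metric models?**
- Correct Weibull model: 45 rejections among 397 defined statistics (11.3%). Other runs, at other sizes and with one third or two thirds treated, gave 9.0%, 9.7%, about 10% and 11.3%. The log HR gaps were about 0.01 or less.
- Scale of that gap at N = 400: expected events are 133.3 x 0.20 = 26.7 and 266.7 x 0.111 = 29.6. The Cox variance is about 1/26.7 + 1/29.6 = 0.071, so the standard error is 0.27. A gap of 0.01 is 0.01/0.27, about 4% of one standard error. It rejects whenever the variance difference is below 0.01^2/3.841 = 0.000026. The denominator is close to zero, which is why the size is unreliable.
- Weibull fitted to lognormal data: 122/388 rejections (31%), although the limiting log HRs differ by only 0.657 - 0.655 = 0.002.
- Exponential fitted to Weibull data: 95 to 97% rejections on a mean gap of about 0.02.
- Weibull fitted to a hazard concentrated in the first days: undefined in 62 to 67% of runs and rejecting in only 27 to 31%.

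The treatment log HR barely responds to a wrong baseline shape, so contrasting it is a weak check on that shape.

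**The case against.** The strongest reply is that the flaw is conditional. Exponential, Weibull and Gompertz models have a PH form, and Royston-Parmar can be fitted on the log cumulative hazard scale. For these, Cox is the consistent estimator and the parametric model the efficient one, which is the usual Hausman setting. The effect measures to be reported are HRs and risk or RMST measures ("Results will be reported with corresponding HRs, ARR, NNT, and RMST differences, stratified by HTI categories"), with no time ratio, so the authors may have had only PH-metric models in mind. This stands. A reader might infer that the test always contrasts different parameters, and the SAP does not support that reading. It does not support the opposite assurance either, because no sentence restricts the models or the metric.

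A reader might also infer that the test is worthless in every case, or that Part III has no other model checks. Neither follows. In the PH case the test carries some information on the parametric baseline. PH itself is examined separately in 3.2, and 3.3 plans AIC, BIC and Cox-Snell checks. It is therefore no fault of the Hausman test that it does not test PH. What remains is that it cannot deliver the robustness 3.5 claims for it. If PH fails and Cox becomes time-dependent, no single log HR is left to compare.

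An undefined statistic would be visible to the analyst and not silently misleading. That is fair and limits the harm. In one setting, taking the absolute value of the negative variance difference produced 91% rejection. The SAP proposes no such step, and I give that figure no weight.

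Finally, no planned estimate or model choice depends on the test, and Part III already asks for cautious interpretation and prospective validation. That bears on severity, not on whether the check works.

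**Conclusion.** The point holds in conditional form. If log-logistic or lognormal is selected and its coefficient is compared with Cox, the Hausman test is undefined or meaningless. The mismatch of sign and scale follows from the model definitions and does not depend on the simulation settings. If a PH-metric model is selected, the test compares like with like. It then rejects a correct Weibull model in about 9 to 11% of runs at nominal 5%, on negligible differences, and it does not examine the hazard shape that fixes the inception points.

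The rejection rates, the share of undefined statistics and the selection frequencies rest on assumed sample size, shape and scale. The estimates in Part III are not invalidated. Severity is minor to moderate: this is one sensitivity item in a secondary analysis, but it is the only one labelled as such.

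**What to change.** In Part III, 3.5, replace the Hausman test as the robustness check with a comparison on a common scale. For each arm and HTI group (HTI = 0, HTI > 0), report day-14 HT risk and RMST to day 14 from the selected parametric model minus the Kaplan-Meier estimate, with bootstrap 95% confidence intervals. These quantities exist for every candidate family and match the ARR and RMST measures already planned in 3.4. RMST responds to when HT occurs as well as to how often. Even so, the two quantities do not by themselves verify the time at which the hazard deceleration curve crosses its threshold, and the text should say so.

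If the Hausman test is kept, limit it to models in PH metric, name the treatment log HR as the coefficient, state what follows from a rejection or a negative variance difference, and label it supplementary. In either case, remove the claim that it secures robustness.

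The cost is a few sentences of SAP text and a short bootstrap. No new data are needed.
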